In more recent years, SRS has been shown to be an effective alternative therapy for patients with brain metastases. It is especially useful in patients with progression of disease following WBRT, for whom treatment-related neurotoxicity is a major concern. SRS allows for the delivery of a highly focused dose of radiation with rapid fall-off and thereby reduces dose to the surrounding normal brain. This feature should potentially reduce the likelihood of developing late neurocognitive deficits, an issue that becomes of increasing concern in long term survivors. SRS has been very well-studied in the setting of brain metastasis. In patients with brain metastases from a variety of primary cancers, SRS has shown to be both safe and efficacious with local control rates of 65-95% and an adverse radiation effect rate of 5-10% (13-15).

In the majority of SRS series, radiosurgery was delivered in a single fraction session. For patients with larger tumors it can be difficult to safely deliver an efficacious dose in a single SRS fraction. RTOG 90-05 (16) was a dose escalation study for patients with previously-irradiated brain tumors, 64% of which were brain metastases. In that study, patients with tumors with a diameter greater than 3 cm and treated to 18 Gy in a single fraction developed \geq grade 3 toxicity at a rate of 50%. The toxicities observed included irreversible edema, which necessitated steroids (15 of 156 patients), radionecrosis that necessitated surgical intervention (16 of 156 patients) or fatality (4 of 156 patients). It was determined that the maximum tolerable dose for these patients was 15 Gy. Tumor control was not reported according to size, but overall local control for all brain metastases was between 25-50% at 12 months, a figure much lower when compared to other SRS series. Therefore, a theoretical argument can be made for fractionation to spare normal tissues while delivering a biologically more effective dose. The advantages of fractionation include reoxygenation of the tumor cells, redistribution of tumor cells into more radiosensitive parts of the cell cycle, and a potential reduction in toxicity due to a lower dose per fraction (17-19).

Davey et al (20) published the outcomes of fractionated SRS for brain metastases in 69 patients. These patients were treated using a surgically attached head frame, meaning the first fraction was delivered at 6 pm on the first day followed by the second fraction at 8 am on the second day. All patients in this trial had tumors less than 3 cm in diameter. The prescription dose was 29.7 Gy prescribed to the 90% isodose line over 2 fractions. The outcomes in this cohort were compared to 35 patients that received 22.5 Gy in a single fraction. The median overall survival for patients treated with 2 fractions

was 30 weeks compared to 16 weeks in the single fraction group. In addition, patients treated with a single fraction were more likely to die due to their brain metastases (43% vs. 28%). Notwithstanding fractionation, other factors that predicted for improved survival were female gender, good performance status, solitary metastasis, and control of extra cranial disease. The authors did not report any toxicity in this paper, but 14 patients required operation for expanding masses, 13 of which were progressing disease and 1 that was radio necrosis.

We have recently reviewed the outcomes in patients treated with fractionated SRS at our institution (manuscript under review). We identified 45 patients with 47 metastases treated to a median dose of 20 Gy (range 13-27 Gy) in 2-3 fractions. With a median follow-up of six months there was an actuarial local control of 80% and 74% at 6 months and 12 months, respectively. These results are similar to the rates reported in single fraction SRS series. We would note, that on average, the tumors were larger in our series compared to others reported. It is also important to note that, compared to the patients treated in RTOG 90-05, our results were superior in terms of both local control (74% vs. 50%) and safety (0% grade 3/4 toxicity vs. 15%). This data supports the use of fractionated SRS in the management of large brain metastases. With that in mind, we propose to determine a safe dose for fractionated SRS for large brain metastases, required for Phase II and III trials that will definitively characterize the efficacy of SRS in these patients.

2.0 Objectives

Primary Objective

2.1 To determine the maximum tolerated dose (MTD) and safety of fractionated SRS when treating brain metastases

- Primary Endpoint: Maximum Tolerated Dose: the maximum amount of Gy fractionated stereotactic radiosurgery (FSRS) delivered without significant toxicity

Secondary Objectives

2.2 To evaluate the local control associated with this therapy.

2.3 To evaluate regional intracranial failure associated with this therapy.

2.4 To evaluate the Health Related Quality of Life (HRQL) associated with this therapy.

Secondary Endpoints

- Local control: proportion of patients with Complete Response (CR), Partial Response (PR), or Stable Disease (SD) in the target lesion
- Regional intracranial failure: proportion of patients that develop new lesions outside the target volume
- Health Related Quality of Life (HRQL) measured by Functional Assessment of Cancer Therapy – General (FACT-Brain) assessment.

3.0 Investigational Plan

3.1 Overall design and plan of study

Prior to enrollment, all patients will be evaluated with a physical exam, review of pathology and laboratory values to confirm diagnosis, and baseline imaging studies

3.2 Accelerator

Physicians will treat patients with linear accelerator-based stereotactic radiosurgery system using 6MV photons.

3.3 Doses

Patients received a total dose of 24 to 36 Gy in 3 fractions (8-12 Gy/fx). Dose was escalated between patients as described in Section 7. The MTD has been determined to be 36 Gy at 3 fractions

In determining the radiation dose and fractionation scheme for this protocol, we used the linear-quadratic model for radiation cell killing to “equate” schemes that care the dose/fraction and number of fractions. This concept of biologically equivalent dose (BED) states that the total effect is given by:

$$n \times d \times (1 + d/(\alpha/\beta))$$

where n is the number of fractions and d is the dose/fraction. The “alpha-beta ratio” characterizes the radiation response of a particular tissue; a higher value is indicative of a tissue that responds acutely to the effects of radiation. Due to their highly proliferative nature, most tumors fall into this category.

This first dose scheme (total dose 24 Gy) is biologically equivalent to the previously studied best recommended doses in the literature (15 Gy, one fraction). We would favor treating in three fractions, as opposed to a single dose, to allow more repair of normal tissue, reoxygenation of tumor cells, and redistribution of tumor cells to more radiosensitive parts of the cell cycle. Using small fraction sizes, 8-12 Gy, will also help reduce late effects of radiation therapy. SRS treatment will be given on an every other day schedule, excluding weekends. The prescription dose will be prescribed to the isodose line best encompassing the planning target volume (PTV) depending on the volume of tumor

3.4 Localization, immobilization, and simulation

Patients will undergo CT simulation with intravenous contrast (contrast recommended, but not required). The patient will be set up in the CT scanner using a mesh mask for immobilization of the head while in the supine position. Additionally, an MRI with contrast, with Cyberknife sequences (i.e. ≤ 1.2 mm slice thickness) is required, unless otherwise contraindicated (e.g. implanted ferromagnetic devices etc).

3.5 Treatment Planning

Treatment planning will be carried out using the appropriate radiosurgery treatment planning station. The gross tumor volume (GTV) will be contoured on the fused image set. A ≤ 2 mm will be added for clinical target volume (CTV) or planning target volume (PTV). The treatment will be prescribed to the isodose line that best covers $\geq 95\%$ the planning target volume, which will typically be the 80% isodose line.

3.6 Treatment Delivery

The planning data containing the coordinates of tumor isocenter, will be transferred to the appropriate platform depending on the treating machine. Treatments will be delivered over non-consecutive days, excluding weekends and holidays

3.7 Supportive Care

3.7.1 Prophylactic Anti-Edema Premedication: 1 hr prior to radiation (optional)

3.7.2 Decadron 4mg PO BID through the treatment course and for 1 week post-last SRS fraction

4.0 Patient Selection and Eligibility

4.1 Selection of Patients

Enrollment is defined as the first day of protocol therapy.

4.2 Number of Patients

A total of 25 patients will be enrolled.

4.3 Inclusion Criteria

All patients must meet the following criteria in order to be included in this study.

- a. Male or female patients \geq 18 years of age
- b. A life expectancy of at least 12 weeks with a Karnofsky performance status of at least 70 (Appendix II)
- c. The target lesion(s) can be accurately measured in at least one dimension according to RECIST
- d. No prior radiotherapy to the brain
- e. Previous or concurrent systemic or targeted chemotherapy is allowed
- f. Patients must have an extra-cranial primary tumor diagnosis
- g. Patients will have no more than 3 distinct lesions within the brain. At least 1 lesion must be a minimum of 3cm in greatest dimension, no larger than 5cm which will be treatable by fractionated stereotactic radiosurgery
- h. The additional lesions will each be treated with single fraction stereotactic radiosurgery
- i. Patient may be on steroids or anti-epileptics
- j. Must be aware of the neoplastic nature of his/her disease and willingly provide written, informed consent after being informed of the procedure to be followed, the experimental nature of the therapy, alternatives, potential benefits, side-effects, risks and discomforts
- k. Patients do not need a histologically proven diagnosis of brain mets

4.4 Exclusion Criteria

- a. Symptomatic patients in need of surgery to the “target” lesion
- b. Four or more newly-diagnosed lesions
- c. Prior surgical resection of targeted tumor

- d. Prior WBRT
- e. Primary brain tumor
- f. Pregnant or breast-feeding patients
- g. Primary tumor histology of lymphoma, leukemia, multiple myeloma or germ cell tumor

5.0 TREATMENT EVALUATION, ADMINISTRATION, AND MODIFICATION

5.1.1 *Tissue constraints*

Treatment shall be delivered via linear accelerator (LINAC) commissioned and equipped to deliver stereotactic radiosurgery. Normal tissues and sensitive critical structures (e.g. spinal cord, brainstem, optic nerves, optic chiasm, and pituitary shall be contoured and the dose to these organs limited. Normal tissue constraints are outlined below.

Normal Tissue Constraints	
Organ	Maximum Dose in 3 Fractions
Spinal Cord	18 Gy
Brainstem	20 Gy
Optic Nerves	18 Gy
Optic Chiasm	18 Gy
Pituitary	20 Gy

5.1.2 *Dose Specification, Homogeneity Considerations & Plan Evaluation*

The treatment plan used shall be based on the assessment of the dose-volume histogram (DVH) with attention to coverage of the planning tumor volume (PTV) and critical normal structures.

The prescription dose is the isodose cloud that encompasses at least 80% of the PTV.

No more than 20% of any PTV shall receive doses >110% of its prescribed dose.

No more than 2% of any PTV shall receive <93% of its prescribed dose.

No more than 5% of any normal tissue shall receive doses in excess of 110% of the primary PTV dose.

5.2 *On-Treatment and post-treatment toxicity evaluation*

All patients will be seen prior to each fraction of stereotactic body radiotherapy and their toxicity evaluated by physical examination. Subsequently, patients will be evaluated for toxicity one month later and then every 8 – 12 weeks. Toxicities will be scored by the NCI CTCAE version 4.0. Also see Section 6.0.

5.2.1 Stereotactic Radiosurgery Related-Toxicity

-SRS: Short-term side effects include but not limited to skin reaction, local hair loss, fatigue, nausea, vomiting, headaches, seizures, bleeding, or need for surgery. Long-term side effects are less likely to occur but if they do occur are more likely to be permanent. They include local hair loss, seizures, focal neurologic deficit, bleeding and symptomatic radiation necrosis.

5.2.2 CT-Related Toxicity

The subject will be exposed to radiation associated with the CT scans performed to complete treatment planning. CT scans are routinely performed as standard-of-care for tumor staging and to monitor response to therapy and the radiation dose associated with these diagnostic scans are felt to represent minimal risk. Patients will also receive MRI scans, which have no radiation and therefore no risk.

Claustrophobia: Possible anxiety, claustrophobia, and/or temporary discomfort may occur as a result of being placed in the scanning devices. Subjects will be monitored and removed from the scanner if required

5.2.3 Dose Levels for treatment

The dose levels are:

- 24 Gy in 3 fractions (8 Gy/fx) delivered on a minimum of every other day schedule for up to 2 weeks.
- 27 Gy in 3 fractions (9 Gy/fx) delivered on a minimum of every other day schedule for up to 2 weeks.
- 30 Gy in 3 fractions (10 Gy/fx) delivered on a minimum of every other day schedule for up to 2 weeks.
- 33 Gy in 3 fractions (11 Gy/fx) delivered on a minimum of every other day schedule for up to 2 weeks.
- 36 Gy in 3 fractions (12 Gy/fx) delivered on a minimum of every other day schedule for up to 2 weeks. This has been determined to be the MTD.

5.2.4 Definition of Dose Limiting Toxicities

Adverse Events will be graded for intensity according to the National Cancer Institute Common Toxicity Criteria, CTCAE Version 4.0. For the purposes of achieving the primary objective, which is determining the maximally tolerated dose of fractionated radiation, the dose limiting toxicity (DLT) will be defined as any adverse event that occurs within 60 days of treatment initiation of radiotherapy and meets any of the following criteria:

5.2.4.1

Grade 4 or worse or central nervous system necrosis, or cerebral edema, or encephalopathy, or intracranial hemorrhage, or myelitis, or seizure, or stroke, or,

5.2.4.2

Any toxicity causing radiation therapy to be withheld for more than two weeks that is not due to tumor progression, or,

5.2.4.3

Any other Grade 3 neurologic toxicity which does not improve to grade 2 within 60 days of treatment initiation of radiotherapy, or,

5.2.4.4

Any patient neurologic death within 60 days of treatment initiation of radiotherapy will be considered a DLT unless in the opinion of the study radiation oncologist and neurosurgeon, the death is definitely unrelated to treatment or death is definitely related to disease progression.

6.0 STUDY EVALUATIONS

6.1 Pretreatment Evaluation

The following tests/procedures will be performed in order to ascertain subject eligibility within 28 days prior to registration unless otherwise specified.

- Complete physical evaluation with a performance status, vital signs, height, and weight, and a complete medical history.
- Laboratory evaluation including complete blood counts with a platelet count and blood chemistry (approximately 3 teaspoons or 1 tablespoon).
- CT (computed tomography) Scan of the
- MRI (Magnetic Resonance Imaging) Scan of the brain
- For women of child bearing potential, a urine pregnancy test will be done. If this comes back positive or questionable, a serum pregnancy test will be completed by taking a small sample (about 1 teaspoonful) of blood. Pregnant women, or women who are currently breast-feeding an infant, will not be allowed to take part in this study.

In addition to the procedures listed above, the following Quality of Life questionnaire will be done for research purposes:

- FACT – BR (FACT – BRAIN) - This assessment will take approximately 5 (five) minutes to complete.

6.1.1 Treatment schedule

Parameter	Pre-Study	SRS			30 days post treatment	8-12 weeks post treatment	Q 8 – 10 weeks for 24 months post treatment
		Fx 1	Fx2	Fx3			
History	X	X	X	X	X	X	X
Physical exam	X	X	X	X	X	X	X

Vital Signs	X				X	X	X
Measurement of disease by MRI	X					X	X
Performance Status	X				X	X	X
Hematologic Studies including CBC	X*						
CT Scan for treatment planning	X						
Serum or Urine Pregnancy Test for WOCBP	X						
FACT - Brain assessment	X				X	X	X
DLT Assessment					X	X	X

* Within 30 days of study start

6.2 Evaluation during treatment

The patient will be carefully followed while on active treatment and post-treatment for 24 months, or until death. Evaluation during treatment will consist of the following activities:

- Administration of stereotactic radiosurgery
- Interim medical history and physical examination at baseline and prior to each radiation therapy treatment.

6.2.1 Evaluations for Follow Up

- Patients will be seen in follow-up 30 days post treatment then at 8-12 weeks post-treatment and every 8-12 weeks for 24 months with the following evaluations:
- Complete physical evaluation with a performance status, vital signs, height, and weight, and a complete medical history
- Dose Limiting Toxicity Assessment
- MRI scans at 8-12 weeks post-treatment and every 8-12 weeks for 24 months for assessment of response to therapy and monitoring.
- Administration of Fact-Brain questionnaire 30 days post treatment, 8 -12 weeks post treatment, and at time of each follow-up visit/scan.

6.3 Study procedures

6.3.1 CT Imaging

A CT scan of the brain will be required. This scan will begin the preliminary mapping of the brain lesions. Secondly, a high resolution MRI will be performed to better plan necessary treatment.

6.4 Objective criteria for defining response

6.4.1. Tumor Response on MRI (RECIST)

Measurable Disease Response: CTEP's RECIST guidelines will be followed. A quick reference to the RECIST guidelines can be downloaded at the following URL:

<http://ctep.info.nih.gov/Policies/WordDocs/RCSTF.PH2TEMPF.doc>. (Appendix II)

Patients enrolled in this study must have a measurable brain metastasis which is defined as lesions that can be accurately measured in at least one dimension: [longest diameter to be recorded] on the MRI scan.

The same method of assessment and the same technique should be used to characterize each identified & reported lesion at baseline & during follow-up.

Taking into account the measurement of the longest diameter only for those lesions with size response, response criteria are defined as:

1. Complete Response (CR): the disappearance of a target lesion. Any pathological lymph nodes (whether target or non-target) must have reduction in short axis to <10 mm.
2. Partial Response (PR): at least a 30% decrease in the sum of diameters of target lesions, taking as reference the baseline sum diameters.
3. Progressive Disease (PD): at least a 20% increase in the sum of diameters of target lesions, taking as a reference the smallest sum on study (this includes the baseline sum if that is the smallest on study). In addition to the relative increase of 20%, the sum must also demonstrate an absolute increase of at least 5 mm. (Note: the appearance of one or more new lesions is also considered progression).
4. Stable Disease (SD): neither sufficient shrinkage to qualify for partial response nor sufficient increase to qualify for progressive disease, taking as reference the smallest sum diameters while on study.²¹

6.4.1.2 Definition of local control

In this study, patients will be recorded as having a lesion that is locally controlled if they have stable disease (SD), partial response (PR), or complete response (CR) in the target lesion; all of which are defined above. Patients will be recorded as having local failure if they have progressive disease (PD) within the target lesion. Patients that develop new lesions outside the target volume will be coded as having a regional intracranial failure. A distant failure will be defined as new brain metastases outside of the treatment volume.

6.4.1.3

HRQL studies (Fact-Brain) will be completed prior to treatment, and following treatment to coincide with follow-up exams and MRI scans. See appendix III for a full version of the Fact-Brain questionnaire.

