7.3.2 Analysis of Secondary Endpoints

2. The proportion patients experiencing local control at each dose will be calculated with 95% exact confidence intervals. The dose-response function, describing the probability of local control at each dose, will be estimated using logistic regression, along with likelihood ratio profile confidence intervals.
3. The probability of failure will be analyzed in a similar fashion to the probability of intracranial failure.
4. The analysis of HRQL data (Section 6.5.1.4) will be descriptive. The data will be summarized by question at each time point with the frequency and percentage of each quality level. For each patient, the trajectory of the score will be plotted against time.

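### Local failure is scored on diameter alone, so a treated lesion shown by pathology to be necrosis only would still be recorded as tumor failure

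*Combined protocol and SAP*

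**What the plan says.** Section 6.4.1.2 calls a lesion controlled if it shows stable disease, partial response or complete response. For failure it says: "Patients will be recorded as having local failure if they have progressive disease (PD) within the target lesion".

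Section 6.4.1 defines progression as "at least a 20% increase in the sum of diameters of target lesions, taking as a reference the smallest sum on study", and adds that "the sum must also demonstrate an absolute increase of at least 5 mm". Under Section 4.3(g) the lesion that qualifies a patient is large: "At least 1 lesion must be a minimum of 3cm in greatest dimension, no larger than 5cm".

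Section 7.3.2 analyses local control by dose. Besides per-dose proportions with exact intervals, it plans a model: "The dose-response function, describing the probability of local control at each dose, will be estimated using logistic regression".

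The protocol treats necrosis and tumor growth as different events in three places:
- The background, describing a two-fraction series, reports that "14 patients required operation for expanding masses, 13 of which were progressing disease and 1 that was radio necrosis".
- Section 5.2.1 says of long-term effects: "They include local hair loss, seizures, focal neurologic deficit, bleeding and symptomatic radiation necrosis".
- Section 5.2.4.1 names necrosis among the dose-limiting events: "Grade 4 or worse or central nervous system necrosis, or cerebral edema".

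Appendix I requires a repeat assessment before complete or partial response is assigned, and suggests tissue work-up where complete response is in doubt. Its note on physician opinion and a review panel concerns non-target lesions. It has no corresponding check on progression in a target lesion.

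**The concern.** An irradiated metastasis can enlarge because tumor is growing or because tissue is necrosing, and diameter cannot separate the two. A site that follows the text must record local failure for a lesion that was resected and found to be necrosis only. The rule then gives an answer that the pathology report contradicts.

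Local control is the first secondary endpoint and is regressed on dose. A miscoding rate that is constant across doses would mainly lower the level. One that rises with dose would bend the slope downward, and could shrink, cancel or reverse a real gain in control. The plan expects dose-limiting toxicity in general to rise with dose (Table 7.1, 0.08 at 24 Gy to 0.20 at 36 Gy). It gives no separate figure for necrosis.

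**Working it through.** The plan states no figure that depends on this definition, so there is none to reproduce. The checks below are of the rule, its possible size, and its overlap with the toxicity endpoint.

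**1. What triggers failure (Section 6.4.1).** Required growth = max(20% of the smallest measurement, 5 mm).
- Smallest measurement 30 mm: 6 mm. For 40 mm: 8 mm. For 50 mm: 10 mm.
- The 5 mm floor governs only below 25 mm, since 0.20 × 25 = 5.
- Because the reference is the nadir, a 40 mm lesion that shrinks to 25 mm and then measures 30 mm is a failure (growth 5 mm, 20%), although it is 25% smaller than at baseline.

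**2. Effect on the level (illustration).** Assumption: 5-10% of truly controlled lesions enlarge past the threshold through necrosis. The range is borrowed from the background's rate for all adverse radiation effects, so it is not an estimate of this event. Recorded control = true control × (1 − miscoded fraction).
- True 80%: 0.80 × 0.95 = 76%; 0.80 × 0.90 = 72%.
- True 74%: 0.74 × 0.95 = 70%; 0.74 × 0.90 = 67%.

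Patients miscoded, of the 25 in Section 7.4: with 20 controlled, 20 × 0.05 = 1 to 20 × 0.10 = 2. If the rate applies to all patients, 25 × 0.05 = 1.25 to 25 × 0.10 = 2.5. That is about 1 to 3 patients. On the second basis the chance of at least one is 1 − 0.95^25 = 72% to 1 − 0.90^25 = 93%.

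With an assumed 5 patients at a dose, one miscoded case moves 4/5 (80%, exact 95% CI 28-99%) to 3/5 (60%, 15-95%).

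**3. Effect on the slope (all inputs assumed).** Let true control rise from 75% at 24 Gy to 85% at 36 Gy, a gain of 10 points.

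| Miscoded fraction, 24 to 36 Gy | Recorded at 24 Gy | Recorded at 36 Gy | Recorded change |
|---|---|---|---|
| 5% to 10% | 0.75 × 0.95 = 71.3% | 0.85 × 0.90 = 76.5% | +5.3 points |
| 8% to 20% | 0.75 × 0.92 = 69.0% | 0.85 × 0.80 = 68.0% | −1.0 point |
| 5% to 20% | 0.75 × 0.95 = 71.3% | 0.85 × 0.80 = 68.0% | −3.3 points |

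The second row borrows the end values of Table 7.1, which cover every dose-limiting toxicity. The direction is the same in each row; the size depends entirely on the assumption.

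**4. Overlap with the DLT endpoint.** Take the first fraction as day 0. The DLT window is stated in three ways: 60 days from the first fraction (5.2.4), 60 days after the last (7.1.1), and ten weeks from the first (7.2.4). The first response MRI is 8-12 weeks after treatment (6.2.1).

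| Last fraction | Window ends (5.2.4 / 7.1.1 / 7.2.4) | First response MRI |
|---|---|---|
| Day 4 | Day 60 / 64 / 70 | Days 60-88 |
| Day 14 | Day 60 / 74 / 70 | Days 70-98 |

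Scheduled imaging overlaps the window by 0 to about 10 days.

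**The case against.** **RECIST is a published standard, and most growth is tumor.** In the cited two-fraction series, 13 of the 14 operated masses (93%) were progression. The 16 of 156 with necrosis needing surgery (10.3%) had been irradiated before, which Section 4.3(d) excludes here. The institution's own fractionated series reports no grade 3/4 toxicity. All this stands: the problem may be uncommon, and its rate cannot be read from the documents. It does not defend a rule that overrides pathology in the case where pathology exists.

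**Subtracting 5-10% from the institution's 80% and 74% would be unsound.** The background does not say how control was scored in that series. This is right, so those values serve above only as hypothetical true rates.

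**The dose-response is uninformative anyway.** With 5 patients per dose (assumed) and true control rising from 75% to 85%, a likelihood ratio test at the 5% level detects the slope about 8% of the time with perfect classification, and about 6% under the third row of the slope table. So correcting the endpoint will not give the regression useful power. The per-dose proportions and the overall level are still reported, and they should describe tumor control.

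**Requiring confirmation as the main definition creates new problems.** Necrosis that stays above the threshold still meets it at the next scan. Salvage between scans needs a rule. Disease progression is a removal criterion (8.1.1), so the next MRI is not assured. The MTD is already declared (3.3, 5.2.3). These arguments stand, and they confine persistence to a sensitivity analysis.

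**A stronger reading to avoid.** A reader might infer that one necrosis counts against a dose twice, as toxicity and as lost control. The documents do not support that as a general statement. The DLT window closes around the first response MRI, and symptomatic necrosis is listed as a long-term effect. The schedule in 6.1.1 lists DLT assessment at later visits, but the definitions in 5.2.4 and 7.1.1 limit which events count. Local control also plays no part in the allocation rule (7.2.2, 7.2.3), so dose selection is not penalised twice. A double count would need necrosis detected at the edge of the window, or detected earlier and also meeting progression on a response scan.

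**Conclusion.** The point holds as a cheap improvement. Local failure rests on diameter alone, with no tissue or confirmation check, so necrosis that reaches the threshold is recorded as tumor failure even against pathology. Necrosis that does not reach it is not miscoded.

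The bias in the dose-response is conditional: it runs downward at higher doses if such necrosis rises with dose, which is plausible but not quantified in the documents. On the assumed 5-10%, a true 80% reads 72-76%, with about 1 to 3 of 25 patients miscoded. Neither the MTD nor the primary analysis depends on this definition.

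**What to change.** In Section 6.4.1.2, add: when tissue removed for clinical reasons from a lesion meeting progression shows necrosis without viable tumor, local failure is not coded. The event is recorded as an adverse event under CTCAE, and counts as a DLT only if it meets Section 5.2.4.

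In Section 7.3.2:
- Report local control by dose under this rule and under the current size-only definition.
- As a further sensitivity analysis, require progression to persist at the next scheduled 8-12 week MRI. Count as failure any progression with no later MRI or tissue, and any lesion given salvage treatment before the next scan, unless tissue shows necrosis only.

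The cost is a few sentences and extra tabulations, using scans already scheduled and pathology from routine care. The limits are:
- Necrosis without tissue that stays at or above the threshold is still counted as failure.
- The change comes after the MTD was declared and must be labelled as such.
- Removal for progression in Section 8.1.1 must be reconciled with continued MRI follow-up.
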